#### **Overview of analytic plan:**

The primary hypothesis for this trial is that suvorexant is superior to placebo in reducing subjective total sleep time at 3 months of treatment in patients with insomnia and suboptimally controlled Type 2 diabetes. The primary endpoint is the change in total sleep time as determined by subjective reporting measures (sleep diaries) from baseline to the 6-week and 3-month follow-ups, adjusted for subjective total sleep time at baseline, consistent with the SPCD statistical approach. Key secondary endpoints include subjective wake after sleep onset and ISI. Exploratory analyses will examine the effect of suvorexant relative to placebo on other sleep continuity parameters (sleep efficiency, sleep quality, sleep latency), HbA1c levels, inflammatory markers, mood, and diabetes-related quality of life, as well as the correlation between the change in the subjective total sleep time and each exploratory endpoint.

#### **Study endpoints:**

The primary outcome (subjective total sleep time) and all secondary and exploratory measures are continuous variables. Primary analyses will focus on the difference from the baseline total sleep time (in minutes) to the final total sleep time evaluated after 6 weeks and 3 months of treatment, consistent with SPCD statistical analyses. The key secondary variables are the difference from baseline to either the 6-week visit or the 3-month (Final Treatment) visit (based on SPCD analyses) in: 1) subjective wake after sleep onset and ISI.

Exploratory analyses will similarly focus on the differences from the baseline value to the final observed value of each outcome evaluated after either 6 weeks or 3 months of treatment (based on SPCD analyses). As these are exploratory analyses, no p-values will be determined other than as described below in the hierarchical testing. These endpoints include:

1. PSQI
2. Subjective SOL, sleep efficiency and sleep quality
3. Depressive symptoms (BDI Score) and quality of life measures (DQOL, Diabetes distress scale)
4. HbA1c
5. Inflammation markers (e.g., C-Reactive Protein)

### **STATISTICAL METHODS**

### **Primary analysis:**

The primary analysis will be based on a weighted average of effects of the change in subjective total sleep time as a function of randomization assignment. Diagnostic methods will be used for all variables to assess their distributional assumptions and to examine potential outlying or influential data points. This analytical method will similarly be used to assess secondary outcomes.

The primary outcome analysis will use the intention-to-treat principle and include all participants who received at least one dose of study medication and completed at least two weeks of sleep diaries following randomization. In addition to the primary and key secondary end points, other secondary end points will be tested in sequential order to control for multiplicity, with an overall type 1 error rate of 5%. Following the primary and key secondary outcomes, the order will be: HbA1c, then CRP. No adjustments for multiple comparisons will be made for additional secondary end points, and thus, statistical probability will not be tested for these variables.

Per-protocol analyses will be repeated on the subgroup of subjects that achieve 85% medication adherence based on the number of pills returned at the 6-week and 3-month visits. Variables related to subjective total sleep time will be determined by Pearson correlation and simple regression analysis using weighted least squares. Those significant contributors will then be input into a stepwise multiple linear regression analysis to identify independent determinants of the change in total sleep time. A two-sided P value <0.05 will be considered significant.

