### Secondary Aims:

- To determine the effect of suvorexant on subjective wake after sleep onset and ISI.
- To assess correlations of subjective total sleep time (TST) with changes in HbA1c levels, other subjective sleep endpoints, ISI, PSQI, inflammatory markers, mood, and diabetes-related quality of life measures.

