### **Key secondary and exploratory analyses:**

Analyses of the key secondary and exploratory endpoints will be conducted using a weighted average of effects from the two 6-week periods, based on randomization assignment. Exploratory correlational analyses will be performed using simple Pearson or Spearman correlations between the change in the subjective total sleep time and secondary and exploratory endpoints.

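### The P<0.05 screen followed by stepwise regression cannot support a claim of independent determinants of sleep-time change, and it needs reconciling with the plan's limit on p-values.

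*Combined protocol and SAP*

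**What the plan says.** Section VIII, Primary analysis, sets out three steps.

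- Screen: "Variables related to subjective total sleep time will be determined by Pearson correlation and simple regression analysis using weighted least squares".
- Selection: "Those significant contributors will then be input into a stepwise multiple linear regression analysis", the stated purpose being "to identify independent determinants of the change in total sleep time".
- Threshold: "A two-sided P value <0.05 will be considered significant".

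For this model the plan gives no candidate list, entry or removal rule, definition of the weights, choice of stage of the sequential parallel comparison design (SPCD), multiplicity control or validation. The analysis set is also unclear, because the paragraph opens with the per-protocol subset.

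Four other places bear on it.

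- Study endpoints, on the exploratory endpoints: "As these are exploratory analyses, no p-values will be determined other than as described below in the hierarchical testing".
- The hierarchy in Primary analysis runs from the primary and key secondary outcomes to HbA1c and then CRP. It contains no correlation or regression. The same paragraph says further secondary end points will not be tested.
- The Overview of analytic plan places the TST correlations among the exploratory analyses, whereas Secondary Aims lists them as an aim: "To assess correlations of subjective total sleep time (TST) with changes in HbA1c levels".
- Key secondary and exploratory analyses plans, separately, "simple Pearson or Spearman correlations between the change in the subjective total sleep time" and the other endpoints, with no selection step.

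**The concern.** A variable reaches the final model only because its sample correlation with TST was large enough to pass a test in these same data. The model then reports a p-value, interval and coefficient as if the variable had been chosen beforehand. Three problems follow: an inflated chance that an unrelated variable is named, coefficients biased away from zero for variables that are named, and a label that claims more than a selected correlation can show.

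The label matters here because the Background motivates the trial by a link between sleep and glycemic control. It leans in part on one correlation (r=0.66, p=0.0360) from a study that the plan itself describes as small. If HbA1c or CRP came out of this procedure as a determinant, it would probably be quoted as evidence for that link.

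**Working it through.** The documents give no error rate or sample size for this regression, so there is no plan figure to reproduce.

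**Inputs**

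- Threshold 0.05, two-sided (Primary analysis).
- n=62, the expected completers (Power/Sample Size). This is an assumption, as the analysis set is not stated; 52 and 72 were also tried.
- Number of candidates k, not stated and therefore assumed:
  - k=9: the exploratory list under Study endpoints, namely PSQI, sleep onset latency (SOL), sleep efficiency, sleep quality, BDI, DQOL, Diabetes Distress Scale, HbA1c and CRP.
  - k=11: the same with wake after sleep onset (WASO) and ISI.
  - k=5: the non-sleep measures only, namely BDI, DQOL, Diabetes Distress Scale, HbA1c and CRP.
- Correlation between candidates, assumed 0 to .5.
- Unweighted least squares, because the weights are not defined.

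**Chance of at least one false determinant, all candidates null**

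The stepwise step cannot empty the list. If elimination reaches a single variable, that variable has already passed at 0.05 on its own. The chance is therefore that of at least one variable passing the screen. For uncorrelated candidates it is 1 − 0.95^k:

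- k=5: 1 − 0.774 = 0.226
- k=9: 1 − 0.630 = 0.370
- k=11: 1 − 0.569 = 0.431

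For correlated candidates it was simulated (10,000 runs at n=62; screen at 0.05, then backward elimination at 0.05):

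| Candidates | correlation 0 (formula) | .3 | .5 |
|---|---|---|---|
| 5 | 23% | 21% | 18% |
| 9 | 37% | 33% | 27% |
| 11 | 43% | 38% | 30% |

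Repeat simulations differ by about one percentage point. A forward stepwise version (enter at 0.05, remove at 0.10) with 9 to 11 candidates and correlations from .6 to 0 gave 24–43% at n=52, 24–44% at n=62 and 24–43% at n=72. The number of candidates drives the rate; sample size hardly matters.

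**Inflation of a real but modest correlation**

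At n=62 the screen passes |r| above t/√(n − 2 + t²) = 2.000/√(60 + 4.00) = 0.250. In simulation a true r of .20 passes about 35% of the time. Among those passes the mean reported r is .33, against .20 over all runs.

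**Candidates that are not null**

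WASO, SOL and sleep efficiency come from the same diary as TST, and sleep efficiency is calculated from it. ISI and PSQI overlap with it in content. For these measures the error is not a chance finding. They are partly the outcome measured again, so they cannot be its independent determinants.

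**The p-value rule**

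The Overview makes the TST correlations exploratory. Study endpoints allows exploratory p-values only within the hierarchy, and the hierarchy has no correlation or regression in it. A screen at P<0.05 cannot be run without p-values. Read plainly, the passages conflict.

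**The case against.** The strongest reply is that this step is peripheral. Secondary aim 2 is already served by the unselected correlations under Key secondary and exploratory analyses. The TST–HbA1c correlation will be computed whatever the stepwise model keeps, and the inflation from .20 to .33 does not touch it. That stands. A reader might infer that the aim itself is compromised, or that the treatment tests are; the documents support neither.

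A reader might also infer that the trial will report false determinants. The percentages above are risks, conditional on assumed candidate counts and on all candidates being null. The screened variables could even be baseline characteristics, since none are listed. Nor is the small sample the cause: more patients would not lower the false-selection rate.

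The limit on p-values follows a sentence about changes from baseline in each endpoint, so it could be meant for treatment comparisons only. That reading is possible, but the text does not say so, and the correlations are classed as secondary in one place and exploratory in another. The sections need reconciling on either reading.

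Two further criticisms are weaker.

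- **Arm.** Leaving arm out of a correlation is not in itself an error. If treatment shifted both variables by 0.4 SD with equal arms, it would add only 0.04/1.04, or about .04, to r.
- **Double records.** Counting re-randomized patients twice matters only if records from both stages are used as independent, which the plan does not state. Assuming 25 patients with two records and 37 with one, simulated type I error for a correlation was 5.7–9.3% at within-patient correlation .3 to .8.

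**Conclusion.** The concern holds for the screening and stepwise step. Under the stated assumptions, the chance of naming at least one false determinant is about 18–23% for the five non-sleep measures and 27–43% for 9 to 11 candidates, roughly four to nine times the nominal 5%. Modest real correlations that survive are overstated by about two thirds (.33 against .20). Where the candidates are other sleep measures, the label is circular whatever their p-values. The conflict with the p-value rule holds on the plain reading and is an ambiguity at the least. The primary SPCD test, the key secondary tests, the HbA1c and CRP treatment comparisons and the unselected correlations stand as planned. This should be changed, but it does not threaten the trial's main result.

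**What to change.** In Primary analysis, delete the significance screen, the stepwise model and the independent-determinants wording. For secondary aim 2, rely on the correlations already planned under Key secondary and exploratory analyses, with these additions:

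- List the endpoints in advance and report all of them, each with a 95% confidence interval and no selection by significance.
- Beside each, give an estimate adjusted for treatment arm and baseline values.
- State which stage or stages supply the records. If both do, use participant-clustered or bootstrap intervals.
- Class these correlations the same way in Secondary Aims and in the Overview, and say whether the limit on p-values covers associations as well as treatment comparisons.

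The cost is SAP wording and modest code, with no extra patients or data. The trial gives up a determinants claim that this procedure could not support.

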### **Key secondary and exploratory analyses:**

Analyses of the key secondary and exploratory endpoints will be conducted using a weighted average of effects from the two 6-week periods, based on randomization assignment. Exploratory correlational analyses will be performed using simple Pearson or Spearman correlations between the change in the subjective total sleep time and secondary and exploratory endpoints.

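### Correlating change in diary total sleep time with WASO, sleep latency and sleep efficiency from the same diary gives largely built-in coefficients

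*Combined protocol and SAP*

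**What the plan says.** The second of the two Secondary Aims in Section II is "To assess correlations of subjective total sleep time (TST) with changes in HbA1c levels, other subjective sleep endpoints, ISI, PSQI, inflammatory markers, mood", followed by diabetes-related quality of life. In Section VIII, the Overview of analytic plan places the correlations among the exploratory analyses, "as well as the correlation between the change in the subjective total sleep time and each exploratory endpoint". The subsection Key secondary and exploratory analyses gives the method: "simple Pearson or Spearman correlations between the change in the subjective total sleep time and secondary and exploratory endpoints".

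The endpoints covered are of two kinds.

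- **From the diary.** "Key secondary endpoints include subjective wake after sleep onset and ISI", and the exploratory list under Study endpoints has "Subjective SOL, sleep efficiency and sleep quality". TST itself is measured "as determined by subjective reporting measures (sleep diaries"). Inclusion criterion 10 takes TST, SOL and WASO from the same nightly logs, and Section V takes all baseline subjective sleep measures from one two-week diary period.
- **Not from the diary.** ISI, PSQI, HbA1c, CRP, and "Depressive symptoms (BDI Score) and quality of life measures (DQOL, Diabetes distress scale").

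The Primary analysis subsection adds a related step. Variables related to TST are found by Pearson correlation and simple regression, and the significant ones enter a stepwise model meant to identify independent predictors of TST change. The significance level is two-sided 0.05.

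The plan does not say how TST or efficiency is computed from the diary. Nor does it say whether the correlations are run by arm, adjusted for arm, or based on one or both six-week periods.

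**The concern.** SOL and WASO are wake time within the period in bed, and efficiency is ordinarily TST divided by time in bed. A change in any of them is then largely a change in TST seen from another side, so a sizeable coefficient is expected whatever the drug does and zero is not the right reference value.

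The correlation that motivates the trial is TST change with HbA1c change. Section I reports r = 0.66 for it in the eszopiclone group of an earlier study. Setting it beside coefficients that are large by construction invites misreading. In the stepwise model the effect would be more direct: diary components are not excluded from the screen, would probably pass it, and could then be reported as determinants of the quantity they make up.

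**Working it through.** The plan states no figure for these correlations, so there is none to reproduce.

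**Inputs from the documents:** 62 completers and effect sizes of 0.36, 0.40 and 0.67 (Power/Sample Size); 72 randomized 1:2, so 48 to placebo.

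**Assumed inputs, not in the documents:** TST = time in bed - SOL - WASO; efficiency = TST / time in bed; changes in the three components mutually independent with no drug effect; SD of change 25 min (SOL), 35 min (WASO) and 0 to 60 min (time in bed, TIB); baseline means 480 min (TIB), 50 min (SOL) and 75 min (WASO).

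**1. Built-in correlation.** With independent components,

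r(TST, WASO) = -SD_WASO / sqrt(SD_TIB² + SD_SOL² + SD_WASO²), and likewise for SOL.

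At SD_TIB = 30: sqrt(900 + 625 + 1225) = 52.4, so r = -35/52.4 = -0.67 for WASO and -25/52.4 = -0.48 for SOL. Efficiency is a ratio and was simulated (n = 62, 1,500 runs per setting).

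| SD of TIB change (min) | WASO | SOL | Efficiency (simulated) |
|---|---|---|---|
| 0 | -0.81 | -0.58 | 1.00 |
| 15 | -0.77 | -0.55 | 0.97 |
| 30 | -0.67 | -0.48 | 0.91 |
| 45 | -0.56 | -0.40 | 0.85 |
| 60 | -0.47 | -0.34 | 0.82 |

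The 5% critical value at n = 62 is tanh(1.96/sqrt(59)) = 0.25. Simulated coefficients exceeded it in 98-100% of runs for WASO, 80-100% for SOL and 100% for efficiency.

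**2. TST reported separately, with its own error.** Add independent error of SD 80 min to the TST change (SD_TIB = 30): sqrt(2750 + 6400) = 95.7, so r = -35/95.7 = -0.37 for WASO and -25/95.7 = -0.26 for SOL. Efficiency computed from that TST inherits the error; its simulated correlation is 0.97.

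**3. Does splitting by arm help?** No. At SD_TIB = 30 the simulated TST-WASO correlation within the drug arm alone averages -0.66.

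**4. An endpoint that is not a component.** An HbA1c change generated independently of the diary gives a mean r of about 0.00 and about 5% rejections. Nothing is built in.

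**5. Ignoring arm.** If the drug shifts both variables by d SD with no link within arms, two equal arms pooled give |r| = (d²/4)/(1 + d²/4):

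- d = 0.36: 0.0324/1.0324 = 0.03
- d = 0.40: 0.04/1.04 = 0.04
- d = 0.67: 0.112/1.112 = 0.10

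Simulated rejections for HbA1c were 6% at d = 0.40 and 13% at d = 0.67.

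**6. Stacking both periods as independent.** With an assumed 62 + 29 records, a nominal 5% error becomes 5.5%, 7% and 10% when the within-person correlation is 0.3, 0.5 and 0.8 in both variables. As a limiting case, assume 50% non-response (24 of 48 placebo patients contribute twice) and identical values in both periods. The effective number is 96²/(48×1² + 24×2²) = 9216/144 = 64, and sqrt(64/96) = 0.82, so the standard error would be about 18% too small.

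**The case against.** The strongest reply has three parts.

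**The identity is not in the documents.** This stands. Inclusion criterion 10 is compatible with a TST that patients report directly. The size is therefore conditional on how TST is derived and on the assumed SDs. Independence is also only a reference case: if patients who lie awake longer also stay in bed longer, the TST-WASO correlation shrinks. That is a further reason why the coefficient cannot be read against zero. Separate reporting does not remove the coupling, as step 2 shows.

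**The analysis is exploratory.** This largely stands. Section VIII labels the correlations exploratory, and Study endpoints rules out p-values for exploratory analyses outside the hierarchy. Suvorexant's effects on WASO, SOL and efficiency are assessed separately, by randomized assignment. The reply does not cover the stepwise model, whose screen is by significance at 0.05 and sits uneasily with the no-p-value rule.

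**Most correlates are unaffected.** This stands. A reader might infer that the whole aim can show nothing about suvorexant or sleep. The documents do not support that: HbA1c, CRP, BDI, DQOL, Diabetes Distress, ISI and PSQI are not diary components, and diary sleep quality is not an arithmetic part of TST.

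A reader might also infer that the plan pools arms and stages for these correlations, and that pooling makes them strong. Neither follows. The pooling of stages described in Section IV concerns the design in general, and the weighted average in Section VIII concerns treatment effects; for the correlations the text is silent. Pooling arms would add only 0.03 to 0.10 at the planning effect sizes.

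**Conclusion.** The point holds for the diary components only, and it is minor. If TST is or closely tracks time in bed minus SOL minus WASO, the planned correlations of its change with WASO, SOL and efficiency are largely built in: about -0.5 to -0.8, -0.3 to -0.6 and 0.8 to 1.0 under the assumed SDs and independent changes, and about -0.4 for WASO with large independent reporting error. They would be uninformative entries under a stated secondary aim. The same coupling would carry diary components into the correlation screen and stepwise model under Primary analysis, where it matters more because conclusions are drawn there.

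A secondary gap is that simple correlations are unadjusted for randomized arm, and the plan does not say how the two periods of placebo non-responders are handled. The consequences are modest: a small added correlation from arm, and somewhat overstated precision if both periods are stacked. The primary test and the hierarchical tests are not affected.

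**What to change.** 1. State how TST and sleep efficiency are derived from the diary.
2. Restrict the correlation aim and the screen under Primary analysis to endpoints not derived from the same diary: HbA1c, CRP, BDI, DQOL, Diabetes Distress, ISI and PSQI. Show WASO, SOL and efficiency only as a descriptive breakdown of the TST change.
3. Replace the simple correlations with partial correlations adjusted for randomized treatment and the baseline values of both variables. Arm adjustment deals with step 5 of the working; it does not remove the component coupling, so item 2 is needed as well.
4. Use one record per patient, or a model with stage and patient clustering if both periods are used, and say which.

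The cost is SAP wording and slightly more programming. The downside is that a few planned coefficients are no longer presented as findings.

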### **Power/Sample Size:**

In total, we expect to randomize 72 participants to treatment with 62 completed subjects (31 per treatment group). Using the SPCD calculator, to achieve 80% power to detect an effect size of .40, at a statistical significance level of 0.05, 70 randomized subjects are required.

The intervention effect is based on data from trials of eszopiclone for rheumatoid arthritis and low back pain which, like diabetes mellitus, are chronic medical conditions associated with high rates of insomnia. We believe that these populations are more appropriate for statistical modeling than the primary insomnia population used in previous suvorexant clinical trials. Similarly, our inclusion criterion of wake after sleep time of 45 minutes is more stringent than that used in the suvorexant trials and the same as that in the rheumatoid arthritis clinical trial. Effect sizes for change in total sleep time in the rheumatoid arthritis and low back pain trials with eszopiclone were .36 and .67, and we have thus used a conservative intermediate effect size of .40 for our sample size calculation.

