### **Study Design and projected enrollment:**

This is a parallel, two-arm, double-blind, randomized placebo-controlled 3-month trial using the sequential parallel comparison design (SPCD), investigating the effects of suvorexant 10–20 mg on subjective total sleep time in patients with suboptimally controlled Type 2 diabetes. The SPCD consists of two stages, with data being pooled from both stages. The first phase involves an unbalanced randomization between placebo and active treatment with more patients randomized to placebo. In the second phase, non-responders treated with placebo are re-randomized to either active treatment or placebo. The first stage is a standard parallel comparison design. However, this first stage generates a cohort of placebo non-responders who then enter the second stage where placebo responses will be lower. This design enriches the primary analysis population, reducing the impact of placebo response rates, and allowing trials to be conducted with reduced study sample size without corresponding decreases in statistical power.

All study procedures will be conducted at Massachusetts General Hospital. We expect to consent and evaluate for eligibility up to 120 Type 2 diabetics in order to achieve our projected randomized sample size of 72 patients with Type 2 diabetes. Subjects will be randomized in a 1:2 ratio to suvorexant 10–20 mg or equivalent placebo for six weeks followed by re-randomization of placebo non-responders to either suvorexant or placebo in a 1:1 design; this will allow 62 Type 2 diabetics to complete the trial at 3 months, after allowing for post-randomization drop-outs.

Eligible patients will be randomized to 6 weeks of suvorexant or placebo after an initial 2-week screening period and a two-week screening run-in period to ensure the stability of sleep disturbance. Participants will complete 4 study visits (consent/screening visit, randomization visit, a 6-week visit, and a 3-months-on-treatment visit). In addition, an initial telephone-based screening assessment and 2 interim phone visits (at 1 week and 7 weeks on treatment) will occur. Suvorexant will be started at 10 mg nightly for the first 7 days. If the 10-mg dose is well tolerated but not effective after one week of treatment, as determined by the one-week phone visits (at 1 week and 7 weeks of treatment for those originally randomized to suvorexant and placebo, respectively), the dose can be increased to 20 mg.

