**Randomization:**

Randomization will be used to avoid bias in the assignment of subjects to treatment, to increase the likelihood that known and unknown subject attributes (e.g., demographics and baseline characteristics) are evenly balanced across treatment groups, and to enhance the validity of statistical comparisons across treatment groups. Blinded treatment will be used to reduce potential bias during data collection and evaluation of clinical endpoints. An unblinded research coordinator will be responsible for all re-randomization determinations and communicating with the pharmacy in that regard.

At the Screening Visit, subjects will be assigned a 3-digit subject number, in ascending sequential order beginning with 001. The subject number will be retained by the subject for the duration of the study. The MGH Clinical Trials Pharmacy and unblinded research coordinator will provide and maintain randomization and blinding. Subjects will be randomized to receive either suvorexant or placebo in a 1:2 ratio, and placebo non-responders will be re-randomized to suvorexant or placebo in a 1:1 ratio at the 6-week visit. The re-randomization will be balanced by using permuted blocks of 4. Subject and investigator will be blinded to treatment assignment. Subjects will be randomized sequentially as they qualify for the study.

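### The stated 80% power for an effect of .40 with 70 randomised subjects does not follow from the printed inputs; .40 in both stages without variance reduction gives at most about 55%

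*Combined protocol and SAP*

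**What the plan says.** All references are to the combined protocol and SAP.

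- **Power/Sample Size** gives the claim: "to achieve 80% power to detect an effect size of .40, at a statistical significance level of 0.05, 70 randomized subjects are required". It expects 72 randomised and 62 completers.
- The same section explains the effect size. The source values are given first: "Effect sizes for change in total sleep time in the rheumatoid arthritis and low back pain trials with eszopiclone were .36 and .67". The planning choice is then stated in these words: "we have thus used a conservative intermediate effect size of .40 for our sample size calculation". This is the only planning effect printed, and it is not split by stage.
- **Primary analysis** says "The primary analysis will be based on a weighted average of effects of the change in subjective total sleep time", and that "A two-sided P value <0.05 will be considered significant". No stage weight is given.
- **Randomization** fixes stage 1: "Subjects will be randomized to receive either suvorexant or placebo in a 1:2 ratio". **Study Design and projected enrollment** fixes stage 2: "re-randomization of placebo non-responders to either suvorexant or placebo in a 1:1 design".
- No expected placebo non-response rate, stage-2 effect, standard deviation or baseline correlation is stated anywhere.

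**The concern.** An effect of .40 is modest, and 70 subjects split 1:2 carry little information about it. The second stage adds only the re-randomised placebo non-responders, so it cannot make up a large shortfall unless something else changes between stages.

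The 80% figure is the only printed justification for the sample size. If .40 holds in both stages without variance reduction, the chance of missing it is about 45% at best, not 20%, and a null result could be misread as evidence against an effect of that size. If larger or adjusted effects were entered in the calculator, the trial is powered for something other than the .40 it reports. A reader cannot tell which is the case.

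**Working it through.** **Inputs from the document:** N = 70; effect .40; two-sided 0.05; 1:2 suvorexant to placebo, then 1:1 among placebo non-responders; weighted average of the two stage effects.

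**Assumptions:** unit standard deviation in both stages; the same effect in both stages; uncorrelated stage estimates because of re-randomisation; no dropout. The placebo non-response rate q is not stated, so q = 0.5 and 0.8 are illustrations and q = 1 is the most favourable value possible.

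**Step 1. Information needed** (inverse variance of the effect estimate) for 80% power at .40:

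((1.960 + 0.842)/.40)² = 49.1

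**Step 2. Information available.**

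- Stage 1: I1 = 1/(1/(N/3) + 1/(2N/3)) = 2N/9 = 15.56
- Stage 2: two arms of (2N/3)q/2 each, so I2 = Nq/6, which is at most 11.67

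The total is at most 27.2, about 55% of the 49.1 needed.

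**Step 3. Power.** With a common effect, the best weight is proportional to information. Power is then Φ(.40·√(I1 + I2) − 1.960). At q = 1 this is Φ(2.087 − 1.960) = 55.1%. N for 80% power is 49.1/(2/9 + q/6), rounded up.

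| q | I1 + I2 | Power, optimal weight | Power, weight 0.5 | N for 80%, optimal weight |
|---|---|---|---|---|
| 0.5 | 21.4 | 45.6% | 38% | 161 |
| 0.8 | 24.9 | 51.4% | 49% | 138 |
| 1.0 | 27.2 | 55.1% | 54% | 127 |

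The plan's figure of 70 is therefore not reproduced. The ceiling is 56.2% at N = 72 and 50.2% if only the 62 completers contribute. Changing the stage-1 allocation does not help: the best split gives 55.2%.

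**Step 4. Simulation check.** With 40,000 simulated trials (23 against 47 in stage 1, then 12:12, 19:19 or 23:24) and the optimal weight, power was 45.9%, 51.5% and 55.6%. This agrees with the table.

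**Step 5. What would give 80% at N = 70, two-sided.** Each item is for the optimal weight.

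- *Larger stage-2 effect, .40 in stage 1.* The required value is √((2.802² − .40²·I1)/I2): 0.76 at q = 0.8 and 0.96 at q = 0.5. With .67 in stage 2, power is 62% to 73% over that range, and 79.4% at q = 1 (80.5% at N = 72).
- *Baseline adjustment, .40 on the raw SD scale.* The residual variance must fall to (I1 + I2)/49.1, which is 0.51 at q = 0.8 and 0.44 at q = 0.5. That is a correlation of about .70 to .75.
- *A combination.* Stage-2 effect .67 with correlation .5 (variance factor 0.75) gives 78%, 82% and 85% at q = 0.6, 0.7 and 0.8.
- *A common effect above .40.* It must be 2.802/√(I1 + I2): 0.54 at q = 1, 0.56 at q = 0.8 and 0.61 at q = 0.5.

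**The case against.** The strongest reply is that .40 in both stages with no variance reduction is not what the plan describes. The .40 comes from two outside trials and can be read as a stage-1 effect. The design section expects a "second stage where placebo responses will be lower", and the Overview of analytic plan adjusts the primary endpoint for baseline sleep time. The 55% figure switches both features off. The calculator's inputs cannot be seen, and some input sets do reach 80%.

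Much of this stands: the calculation does not show that the calculator was wrong, or that the planned analysis has 55% power. It does not rescue the printed claim. Over 50% to 80% non-response, the stage-2 effect needed on its own exceeds .67, the larger of the two effects the plan cites. Adjustment on its own needs a correlation that is nowhere stated. If either was assumed, a single effect of .40, described as conservative, is not what the trial was powered for.

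One may also note that the sample size section does not say two-sided, and that the two-sided sentence closes a paragraph that also covers other analyses. A one-sided 0.05 test raises the ceiling only to Φ(2.087 − 1.645) = 67%. It reaches 80% only if combined with a larger stage-2 effect, for example .67 with q of about 0.7 or more.

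The saving from the SPCD is already credited: the calculation counts all stage-2 data, and a plain 1:1 trial at .40 would need about 196 subjects by the same normal approximation, 4·(2.802/.40)².

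**Conclusion.** The concern holds. From the printed inputs, 70 randomised subjects give at most 55.1% power for .40, against the stated 80%. The gap of about 25 percentage points is far beyond rounding or approximation. The result rests on .40 in both stages, unit variance without reduction and a two-sided 0.05 test. Within those terms it holds for any non-response rate and any stage weight. The 46% to 51% range also depends on the assumed 50% to 80% non-response, which is not in the documents.

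What is established is that the stated power does not follow from the stated inputs. Which inputs were actually used remains unknown. Because this is the sole basis for the sample size, it should be corrected before the figure is relied on.

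**What to change.** Keep 72 randomised and revise the Power/Sample Size section:

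1. Retrieve the calculator inputs and check which effect was entered: .40, .67, or different values by stage. One lead, possibly chance: a plain 1:1 two-arm comparison at .67 needs 4·(2.802/.67)² = 69.9, or 70 subjects.
2. Recompute from the planned placebo non-response rate, a prespecified stage weight, the stage-1 and stage-2 effects, the SD scale or baseline correlation, two-sided 0.05, and attrition from 72 to 62.
3. If those inputs give 80%, keep the figure and print them as the assumptions, including any stage-2 effect that differs from .40.
4. If they do not, replace 80% with the recomputed power for .40 (at most about 55% without variance reduction, and lower with dropout), or state the common effect detectable with 80% power (about 0.6).

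The cost is one recalculation and a change of wording. The stated power may become less favourable. No patients are added, and neither conduct nor analysis changes.
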